### **Adverse Event Overview**

The number and percentage of subjects experiencing treatment-emergent AEs will be summarized for the following AE categories.

- AEs
- AEs rated at least possibly related to study drug by the investigator (Probably Related or Possibly Related)
- Severe AEs
- SAEs
- SAEs rated at least possibly related to study drug by the investigator (Probably Related or Possibly Related)
- AEs leading to discontinuation of study drug
- AEs leading to death
- Uveitis-related AEs (see below)
- AEs of special interest (see below)

Uveitis-related AEs will be:

- Loss of transparency of the cornea
- Band keratopathy
- Synechiae
- Cataracts
- Glaucoma/increased intraocular pressure
- Vitreous hemorrhage
- Macular edema
- Retinal detachment
- Epiretinal membrane

- Vitreo-macular traction
- Retinal ischemia
- Vision loss
- Hypotony

The current list of AEs of special interest for treatment with adalimumab is:

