6.1.3 Relationship to Study Drug

The Investigator will use the following definitions to assess the relationship of the adverse event to the use of study drug:

Probably Related	An adverse event has a strong temporal relationship to study drug or recurs on re-challenge and an Other cause of event is unlikely or significantly less likely.
Possibly Related	An adverse event has a strong temporal relationship to the study drug and an Other cause of event is equally or less likely compared to the potential relationship to study drug.
Probably Not Related	An adverse event has little or no temporal relationship to the study drug and/or a more likely Other cause of event exists.
Not Related	An adverse event is due to an underlying or concurrent illness or effect of another drug and is not related to the study drug (e.g., has no temporal relationship to study drug or has a much more likely Other cause of event).

For causality assessments, events meeting the categories of probably or possibly related will be considered "associated." Events that are probably not or not related will be

considered "not associated." In addition, when the Investigator has not reported a causality or deemed it not assessable, AbbVie will consider the event associated.

If an Investigator's opinion of possibly, probably not, or not related to study drug is given, an 'Other' cause of event must be provided by the Investigator for the serious adverse event.

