8.1.5 Analysis of Safety

Treatment-emergent AEs will be summarized using descriptive statistics.

Treatment-emergent AEs are defined as events with an onset date on or after the first study drug administration until 70 days following the last study drug administration. In case of increasing severity of an existing AE, the worsening will be considered as a new AE with a new onset date.

AEs will be tabulated by system organ class and preferred term whereby the most current implemented MedDRA dictionary will be used. Also, summaries by severity and relationship to study drug will be done. Certain AEs, like serious or severe, leading to premature withdrawal, will be listed and described in detail. AEs of special interest for treatment with biologics will be defined in the SAP and analyzed separately.

Other safety variables like laboratory data and vital signs will be described by descriptive statistics as mentioned before. In addition, shift tables and listings will be provided for abnormal values whereby the normal range of the analyzing laboratory will be used.

The IDMC will undertake a comprehensive review and assessment of the cumulative safety data until the completion of Study M10-877 and Study M10-880. Please refer to Section 5.5.5.1 for additional information regarding IDMC review.

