**Adverse Events by System Organ Class and Preferred Term**

The number and percentage of subjects experiencing AEs will be tabulated according to the primary MedDRA SOC and PT for each treatment group. Subjects reporting more than one AE for a given PT will be counted only once for that term (most severe incident for the severity tables and most related incident for the relationship tables). Subjects reporting more than one type of AE within a SOC will be counted only once for that SOC. Subjects reporting more than one type of AE will be counted only once in the overall total.

The following AEs will be summarized using the conventions described above:

- AEs
- AEs rated at least possibly related to study drug by the investigator
- AEs by highest relationship
- AEs by maximum severity
- SAEs
- AEs leading to discontinuation of study drug
- AEs leading to death
- AEs of special interest

A listing of subject numbers associated with AEs by SOC and PT will be provided.

By-subject listings will be provided for AEs at least possibly related to study drug, severe AEs, SAEs, AEs leading to discontinuation, AEs leading to death, and AEs of special interest. In addition, SAEs with onset after informed consent but before the first dose of adalimumab was administered will be considered as pre-treatment SAEs and will be listed separately.

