### **Adverse Events by Maximum Relationship**

Adverse events will also be summarized by maximum relationship to study, as assessed by the investigator. If a subject has an adverse event with unknown relationship, then the subject will be counted in the relationship category of "unknown," even if the subject has

another occurrence of the same event with a relationship present. The only exception is if the subject has another occurrence of the same adverse event with a relationship assessment of "Probably Related" or "Possibly Related." In this case, the subject will be counted under the "Probably Related" or "Possibly Related" category, respectively.

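### The SAP's related-AE and related-SAE outputs leave out events with missing or non-assessable causality, which the protocol treats as associated with study drug

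*SAP*

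**What the plan says.** **Protocol.** Section 6.1.3 has the investigator rate each event on a four-level scale and then groups the ratings: "events meeting the categories of probably or possibly related will be considered" associated, and the two lower levels not associated. It adds a rule for events without a usable rating: "when the Investigator has not reported a causality or deemed it not assessable, AbbVie will consider the event associated". Section 8.1.5 makes relationship a dimension of the analysis: "summaries by severity and relationship to study drug will be done".

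**SAP.** In section 11.1 the Adverse Event Overview has two causality rows:
- "AEs rated at least possibly related to study drug by the investigator (Probably Related or Possibly Related")
- "SAEs rated at least possibly related to study drug by the investigator (Probably Related or Possibly Related")

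The SOC and preferred-term tables reuse the first category ("AEs rated at least possibly related to study drug by the investigator"), and a by-subject listing of related AEs is planned. The overview is also given as events per 100 subject-years, and it is repeated by subgroup and by concomitant-treatment period.

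The paragraph on maximum relationship deals with unrated events: "If a subject has an adverse event with unknown relationship, then the subject will be counted in the relationship category of" unknown. It then relaxes this: "The only exception is if the subject has another occurrence of the same adverse event with a relationship" rating of Probably or Possibly Related.

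Nothing in the SAP counts missing causality as related, and nothing explains why the protocol's rule is not used.

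**The concern.** The two documents give different answers for the same event. An AE with no causality rating is associated under the protocol. Under the SAP it is outside every output described as related. The difference can go only one way, towards fewer drug-related events in the report.

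Long-term safety is the primary objective and every subject receives adalimumab, so no control arm helps with attribution. Readers will use the causality rows for that purpose, and related SAEs are likely to be few enough for a handful of events to be noticeable. The SAP clearly expects some unrated events, because it writes a rule for them. It is also uneven: an AE with an incomplete onset date is presumed treatment-emergent unless there is evidence otherwise, but missing causality gets no comparable cautious default.

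**Working it through.** The plan has no figure to reproduce here. The check compares the two rules and then illustrates the size.

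**Step 1. Apply both rules to the ratings a subject may have for one AE term.**

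| Ratings for the term | SAP 11.1 | Protocol 6.1.3 |
|---|---|---|
| Unrated only | unknown | associated |
| Unrated and Not Related | unknown | associated |
| Unrated and Possibly Related | Possibly Related | associated |
| Not Related only | not related | not associated |

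The rules differ only where an unrated event is not accompanied by a Probably or Possibly Related occurrence of the same term.

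**Step 2. Identify which outputs move.**
- *Events per 100 subject-years (overview):* the numerator counts events, so each unrated event is lost, even if the subject has another related AE.
- *Overview percentages:* these count subjects, so a subject is lost only if no other AE (or, in the SAE row, no other SAE) is rated related.
- *Related-AE SOC/PT table:* each subject counts once per term and once per SOC, so the same logic applies within each term and each SOC.
- *Related-AE listing:* unrated events do not qualify.
- *Maximum-relationship table:* unrated AEs appear as unknown. No table by relationship is listed for SAEs.

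**Step 3. Illustrate the size at subject level.** N = 400 is the protocol synopsis estimate of enrolment. The base counts r and the values of m are assumptions. Here m is the number of subjects whose only potentially related events are unrated.

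Percentage under the protocol rule = (r + m) / N; under the SAP rule = r / N.

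- Related AEs, r = 160 (160/400 = 40.00%): m = 0, 1, 4, 8, 20 gives 40.00%, 40.25%, 41.00%, 42.00%, 45.00%.
- Related SAEs, r = 20 (20/400 = 5.00%): m = 0, 1, 2, 4, 8 gives 5.00%, 5.25%, 5.50%, 6.00%, 7.00%. The relative increase m/r runs from 0% to 8/20 = 40%.

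**Step 4. Illustrate the size at event level.** Let e events be rated related and u be unrated. Subject-years are the same under both rules and cancel, so the relative shortfall in the related rate is u / (e + u). With an assumed e = 20:
- u = 0: 0%
- u = 1: 1/21 = 4.8%
- u = 5: 5/25 = 20%

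**The case against.** The strongest reply is that the documents describe two different variables. The SAP rows report what the investigator said, and as such their label is literally accurate. The protocol sentence describes what the sponsor will consider, and section 8.1.5 does not say that the tables must use the sponsor's grouping. This stands as a point about the label. It does not remove the discrepancy: the protocol rule sits in the general section on relationship to study drug and is not confined to expedited reporting, and no planned output applies it.

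The second reply is that unrated events should be rare. Protocol 6.1 has the investigator record relationship for every AE, the scale in 6.1.3 has no non-assessable level, section 10.1 requires investigator approval of that field when the eCRF is the source, and section 11.0 provides checks and queries. This stands, and it is why the effect must be stated conditionally. A reader might infer that related counts are in fact understated, or might take the 4.8% to 20% above as an estimate. The documents support neither: they give no number of unrated events, that range is an event-level assumption, and it does not transfer to the subject percentages.

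Third, a reader might infer that the SAP hides these events or counts them as unrelated. It does not. Unknown ranks above the two lower ratings in the maximum-relationship table. All SAEs, severe AEs, AEs leading to discontinuation or death, and AEs of special interest are reported and listed whatever their causality. An unrated SAE is therefore listed individually, but it reaches no related-SAE count, and its missing rating is visible only if the listing prints causality.

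Finally, the study is descriptive with no decision rule, and neither document makes related events a formal endpoint. That limits the consequence but does not justify an unexplained difference.

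**Conclusion.** The concern holds in conditional form. SAP 11.1 applies a narrower causality rule than Protocol 6.1.3 without saying so. Whenever unrated events occur, the related-AE and related-SAE rows, the related-AE SOC/PT table and listing, and the related event rates will be lower than under the protocol rule or, for subject counts where another related event is present, equal. They can never be higher.

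The actual size is unknown and may be zero. Under the stated assumptions the shift is modest for related AEs (up to 5 percentage points with 20 affected subjects on a base of 40%) and proportionally larger for related SAEs (5.00% to 7.00% with 8 affected subjects). The conclusion rests on reading the protocol rule as covering AE causality generally, as its placement suggests, and on the absence of any SAP text that adopts or sets it aside.

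**What to change.** In SAP 11.1:
1. Count AEs and SAEs with missing or non-assessable causality as related in the overview rows, the related-AE SOC/PT table, the related rates per 100 subject-years (including the subgroup and treatment-period overviews) and the related-AE listing.
2. Relabel those outputs, for example *at least possibly related per investigator, or causality missing/not assessable*. Without this, the present label would become untrue.
3. Show the number so counted as a sub-row or footnote, for AEs and for SAEs, so that the investigator-rated count can still be read off. The unknown category can stay in the maximum-relationship table, with a note that it counts as related elsewhere.

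If the sponsor prefers a purely investigator-rated row, the SAP should give the reason and add a second row on the protocol rule.

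The cost is a few edits to labels and category rules, with no new data. Related counts may rise slightly; if every event is rated, nothing changes.

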6.1.1.1.1 Uveitis-Related Events

The following events are known complications related to the condition being treated and will be classified as uveitis-related events. These events will be analyzed separately from other adverse events in the final study report.

The following events are not a complete list of all potential uveitis-related events (e.g., choroidal thickening, choroidal detachment, retinal effusion, are not included but could possibly be events related to uveitis). The investigator must determine if a specific event is uveitis-related.

- Loss of transparency of the cornea
- Band keratopathy
- Synechiae
- Cataracts
- Glaucoma/increased intraocular pressure
- Vitreous hemorrhage
- Macular edema
- Retinal detachment
- Epiretinal membrane
- Vitreo-macular traction
- Retinal ischemia
- Vision loss
- Hypotony

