### **4.0                   Study Objectives, Design and Procedures**

#### **4.1                   Objectives**

[figure not shown]
The primary objective of this study is to evaluate the long-term safety of adalimumab 40 mg given every other week (eow) subcutaneously (SC) in subjects with non-infectious intermediate, posterior, or panuveitis who participated in Protocol M10-877 or Protocol M10-880. Long-term efficacy will also be assessed.

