### **Adverse Event Rates per 100 Subject-Years of Study Drug Exposure**

The analysis of AEs per 100 subject-years will be presented for the AE overview, for AEs by SOC and PT, and for SAEs by SOC and PT.

The treatment-emergent AE rate per 100 subject-years of exposure to study drug (ADA) will be calculated. For this calculation, one year will be considered to be 365.25 days. The numerator of the rate will be the total number of AEs reported that a subject can be counted more than once overall. The denominator of the rates will be the total number of days exposed to study drug summed across all treated subjects divided by 365.25. The AE rate per 100 subject-years of exposure will be calculated as  $[(\text{numerator}/\text{denominator})]*100$ . The number of AEs reported (numerator), the total number of years of study drug exposure (denominator), and the AE rate per 100 subject-years will be presented overall.

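### SAP 11.1 closes the uveitis-related AE category at 13 terms, although protocol 6.1.1.1.1 calls that list incomplete and leaves the decision to the investigator

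*SAP*

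**What the plan says.** Protocol 6.1.1.1.1 (Uveitis-Related Events) does three things.

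- It names 13 known complications of the disease, classes them as uveitis-related, and commits to a separate analysis: "These events will be analyzed separately from other adverse events in the final study report".
- It then says the list is open: "The following events are not a complete list of all potential uveitis-related events". It gives three instances outside the list: "choroidal thickening, choroidal detachment, retinal effusion, are not included but could possibly be events related to uveitis".
- It assigns the decision: "The investigator must determine if a specific event is uveitis-related".

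SAP 11.1 makes uveitis-related AEs one of nine rows in the Adverse Event Overview. It defines the row with "Uveitis-related AEs will be", followed by the same 13 terms. There is no wording to show that these are examples, no mention of the investigator's determination, and none of the protocol's three further instances.

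The overview is used again later in SAP 11.1. On exposure-adjusted rates the SAP says: "The analysis of AEs per 100 subject-years will be presented for the AE overview, for AEs by SOC and PT". The section on subgroup analyses of AEs repeats the overview, with percentages and rates, by corticosteroid and immunosuppressant use. It does so again for treatment periods on and off those drugs.

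**The concern.** The two documents give different membership rules for the same category, and the SAP does not say that it departs from the protocol. SAP 4.1 states: "The primary objective of this study is to evaluate the long-term safety of adalimumab". How safety events are grouped therefore bears on the main purpose of the study.

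An investigator who follows the protocol and judges a choroidal detachment to be uveitis-related will find that judgement has no effect on the uveitis-related row. A reader of the report will reasonably take that row to mean what the protocol says it means. Because the row feeds the rates, the subgroup overviews and the treatment-period overviews, a difference in definition carries into all of them.

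The category is also thinly described. It is reported as a total, and SAP 11.1 names no table or listing that would show which events make it up.

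**Working it through.** The plan has no figure to reproduce here. The check is a comparison of the two texts.

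**1. The lists.** Protocol 6.1.1.1.1 has 13 terms and so does SAP 11.1. All 13 match and the SAP adds none. Of the three instances that the protocol names outside its list, none is in the SAP list.

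**2. Is the SAP list opened elsewhere?** The SAP does allow a list to be modified at the time of analysis, but that sentence closes the list of AEs of special interest. No such sentence follows the uveitis-related list. Protocol 8.1.5 hands the definition of AEs of special interest to the SAP; it makes no such delegation for uveitis-related events. Where the SAP wants investigator judgement in the overview, as for relationship to study drug, it says so.

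**3. Which outputs are affected?** The overview row, its rate per 100 subject-years, and the subgroup and treatment-period overviews. Under the heading on AEs by SOC and PT, SAP 11.1 names eight sets for summary tables and six groups for by-subject listings, apart from the pre-treatment SAEs. AEs of special interest are in both; uveitis-related AEs are in neither.

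**4. Direction of the error.** Split the events into three groups:

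- A: listed, and judged uveitis-related by the investigator
- B: listed, but judged not uveitis-related
- C: not listed, but judged uveitis-related

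The SAP counts A + B. The protocol supports more than one target:

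- If listed events always count and the investigator adds others, the target is A + B + C. The SAP is short by C.
- If the investigator decides every case, the target is A + C. The SAP count differs from it by (A + B) − (A + C) = B − C, which may be positive or negative.
- If only the listed events are meant for analysis, the target is A + B and there is no difference.

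The denominator, total exposure, does not depend on the definition. The rate under the second reading is therefore off by 100 × (B − C) / subject-years. The percentage of subjects changes less directly, because a subject counts once per row. It moves only for subjects whose sole qualifying event lies in B or C.

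The documents give neither B nor C, so none of these differences can be put in numbers.

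**5. Was the judgement recorded?** The AE attributes in protocol 6.1 and the AE eCRF segments named in protocol 10.1 (alternate etiology, severity, frequency, relationship to study drug) include no field for it. The documents do not settle whether it exists elsewhere on the eCRF.

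**The case against.** The best defence reads the protocol's first paragraph closely. It classes the listed complications as uveitis-related and promises to analyse those events separately. The statement that the list is incomplete comes in the next paragraph, speaks only of potential events, and makes no analysis promise of its own. On that reading the SAP reproduces all 13 terms and meets the commitment. The reading is possible and the protocol is not free of ambiguity. But it leaves the instruction that the investigator must decide with no role in the analysis, and the SAP does not say that it adopts this reading.

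The defence is right on several other matters, and each rules out something a reader might infer from the mismatch.

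- *That safety events are lost.* They are not. A choroidal detachment still counts among all AEs, appears in the SOC/PT tables, and enters the SAE, discontinuation or death summaries where it qualifies. Intraocular pressure, lens opacity, macular edema and visual acuity also have analyses of their own.
- *That the promised separate analysis is absent.* The row has its own percentages, rates and subgroup output, so a rate per 100 subject-years is already planned. What SAP 11.1 lacks is a breakdown by event and a listing. Even that is qualified, because SAP 12.0 places the list of outputs in a separate document that is not available here.
- *That the count must be too low.* This would need B to be zero, or the first of the three readings to be the right one. The documents establish neither.

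The study is also single-arm and descriptive, and no test or decision rule rests on this row.

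**Conclusion.** The mismatch stands. SAP 11.1 fixes the membership of a safety category that the protocol leaves open and assigns to the investigator, and it does so without declaring a departure. As written, an investigator-identified event outside the 13 terms is left out of the uveitis-related row, its rate, and the subgroup and treatment-period overviews.

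The effect is confined to one of nine overview categories and is one of classification. Neither its size nor its sign can be determined: B and C are unknown, and the protocol does not say whether the investigator may reject a listed term. A reader might conclude that uveitis-related events will be under-reported. The documents support only that they may be grouped differently from what the protocol describes.

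The conclusion assumes that the SAP wording is applied literally and that the unseen programming document does not widen the category. It should be corrected because it concerns the primary objective and the correction is cheap.

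**What to change.** First confirm whether the AE eCRF captured the investigator's uveitis-related determination.

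**If it was captured**, amend SAP 11.1 as follows:

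- Define uveitis-related AEs as the 13 terms plus any other AE that the investigator identified as uveitis-related.
- Show the two components separately, so that the list-based count stays visible.
- State how a listed term judged not uveitis-related is handled.
- Add uveitis-related AEs to the SOC/PT summaries and to the by-subject listings. No new rate analysis is needed, since the planned rates follow the corrected row.

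**If it was not captured**, keep the fixed list, declare it in the SAP as a departure from protocol 6.1.1.1.1, and label the category as list-based in every table that uses it.

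The cost is the SAP wording, one extra table and one listing. The count may change. Recovering the investigator's judgement where it was not recorded would be a larger task, and the second option avoids it.
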